7. STUDY MEDICATION

7.1. Overview of Investigational Drug

7.1.1. Access to investigational drug

SHR-1210 is manufactured by Suzhou Suncadia Biopharmaceuticals Co., Ltd.

7.1.2. Dosage form, packaging, and label of investigational drug

Investigational drug: SHR-1210 Injection

Manufacturer: Suzhou Suncadia Biopharmaceuticals Co., Ltd.

Dosage form: lyophilized powder

Strength: 200 mg in 20 mL vials

Batch no.: see Certificate of Analysis

Method of administration: intravenous drip infusion

Shelf life: 2 years (tentative) from the date of manufacture

Storage conditions: sealed, away from light, stored at 2-8 °C in medical refrigerator. Do not freeze.

Label: refer to the pharmacy manual, and the actual label shall prevail

7.1.3. Storage and stability of investigational drug

The investigators or the authorized representative thereof (e.g., pharmacist) will ensure that all investigational drugs are stored in a secure and access-controlled area conforming to storage conditions and regulatory requirements.

The investigational drug should be stored under the storage conditions listed in Section 7.1.2. Where the protocol differs from other information, SHR-1210 will be stored according to the storage conditions listed on the label.

Daily maximum and minimum temperatures of all storage zones (such as cold storage) must be recorded by study sites. Documentation should begin with the receipt of the investigational drug until the last subject completes the last visit. Even if a continuous monitoring system is employed, a written log must be kept to ensure a correct record of storage temperature. The temperature monitoring and storage devices (such as refrigerator) should be regularly inspected to ensure proper operation.

Any deviations related to the labeled conditions on the product should be immediately reported upon discovery. Study sites should take active measures to restore the investigational drug under the storage conditions described on the label, and the temperature deviation and the measures taken should be reported to the sponsor.

Investigational drugs affected by the temperature deviation should be isolated temporarily and may only be used after approval by the sponsor, and such case is not considered a protocol deviation. The use of affected investigational drugs without the approval of the sponsor is considered a protocol deviation. The sponsor will provide a detailed procedure on reporting temperature deviations to study sites.

7.1.4. Preparation of investigational drug

Drugs used in this study are all administered via intravenous drip infusion. Therefore, these drugs should be prepared by qualified or experienced study staff such as a study nurse. The investigational drug SHR-1210 does not contain preservatives, and must be prepared using aseptic technique. Refer to the pharmacy manual for drug preparation.

7.1.5. Administration of investigational drug

SHR-1210: 200 mg/dose, intravenous drip infusion over 30 min (not less than 20 min and not more than 60 min) on D1 of each 2-week cycle. The treatment will continue until the occurrence of confirmed PD, intolerable toxicity, or other reasons specified in the protocol.

For Cycle 2 and subsequent cycles, the drug can be administered 3 days before or after the day of scheduled administration. Administration beyond 3 days after the scheduled dosing day will be considered as a dose delay. Subsequent dosing will be carried out based on the actual date of the previous dosing. All required examinations and evaluations must be completed prior to each dose.

7.1.6. Dose modification and delay

7.1.6.1. Dose modification

AEs related to SHR-1210 may be immune-related AEs (irAEs), and may develop shortly after the first dose or months after the last dose. SHR-1210 should be interrupted if events listed in the following table occur. During the study, the investigators must consult with the sponsor if, based on the benefit to risk ratio of the subject, SHR-1210 should be interrupted or resumed instead of the recommendations found in [Table 2](#) or when the situation is not listed.

Table 2. SHR-1210 dose modification criteria

Treatment-Related Immune-Related Adverse Event (irAE)	Severity Grade for Treatment Interruption	Resumption	SHR-1210 Treatment
Diarrhea/Colitis	2-3	Recovery to Grade 0-1	Treatment should be discontinued if the AE does not resolve within 12 weeks after the last dose or the dose of corticosteroids cannot be reduced to \leq 10 mg of prednisone or equivalent within 12 weeks.
	4	Discontinuation	Discontinuation
AST, ALT, or bilirubin increased	2	Recovery to Grade 0-1	Treatment should be discontinued if the AE fails to resolve within 12 weeks after the last dose.
	3-4	Discontinuation	Discontinuation

Treatment-Related Immune-Related Adverse Event (irAE)	Severity Grade for Treatment Interruption	Resumption	SHR-1210 Treatment
Hyperthyroidism	3	Recovery to Grade 0-1	Treatment should be discontinued if the AE does not resolve within 12 weeks after the last dose or the dose of corticosteroids cannot be reduced to \leq 10 mg of prednisone or equivalent within 12 weeks.
	4	Discontinuation	Discontinuation
Hypothyroidism		Treatment can be continued after starting thyroxine replacement therapy	Treatment can be continued after starting thyroxine replacement therapy
Pneumonia	2	Recovery to Grade 0-1	Treatment should be discontinued if the AE does not resolve within 12 weeks after the last dose or the dose of corticosteroids cannot be reduced to \leq 10 mg of prednisone or equivalent within 12 weeks.
	3-4	Discontinuation	Discontinuation
Immune-Related Hypophysitis	2-3	Recovery to Grade 0-1; SHR-1210 treatment can be continued after starting endocrine replacement therapy	Treatment should be discontinued if the AE does not resolve within 12 weeks after the last dose or the dose of corticosteroids cannot be reduced to \leq 10 mg of prednisone or equivalent within 12 weeks.
	4	Discontinuation	Discontinuation
Type I Diabetes Mellitus (new onset) or Hyperglycemia	New-onset type I diabetes mellitus or Grade 3-4 hyperglycemia accompanied with evidence of β -cell depletion	After clinical and metabolic conditions are stabilized	Continue SHR-1210 treatment.
Renal Failure or Nephritis	2	Recovery to Grade 0-1	Treatment should be discontinued if the AE does not resolve within 12 weeks after the last dose or the dose of corticosteroids cannot be reduced to \leq 10 mg of prednisone or equivalent within 12 weeks.
	3-4	Discontinuation	Discontinuation
Infusion Reaction	2	Symptoms disappeared	Re-administer at 50% of the initial rate after symptoms resolve. If no reaction occurs within 30 min, restore the original infusion rate (100%). Closely monitor. If the symptoms recur, the administration of the current SHR-1210 dose will be discontinued.
	3-4	Discontinuation	Discontinuation

Treatment-Related Immune-Related Adverse Event (irAE)	Severity Grade for Treatment Interruption	Resumption	SHR-1210 Treatment
Other Treatment-Related AEs	3	Recovery to Grade 0-1	Treatment should be discontinued if the AE does not resolve within 12 weeks after the last dose or the dose of corticosteroids cannot be reduced to ≤ 10 mg of prednisone or equivalent within 12 weeks.
	4	Discontinuation	Discontinuation

Note: Treatment should be discontinued if any Grade 3 treatment-related AE recurs or any life-threatening event occurs.

For patients with metastasis to liver and Grade 2 AST or ALT increased at baseline, treatment should be discontinued if a $\geq 50\%$ increase in AST or ALT from baseline persists for at least 1 week.

For subjects with intolerable or persistent Grade 2 treatment-related AEs, the investigators may consider interrupting SHR-1210 treatment if appropriate. For subjects with persistent Grade 2 adverse reactions that fail to return to Grade 0-1 within 12 weeks after the last dose, treatment should be discontinued.

7.2. Management, Dispensation, and Return of Investigational Drug

Designated personnel are responsible for the management, dispensation, and return of investigational drugs. The investigators must ensure that all investigational drugs are used by enrolled subjects only and the dose and route of administration comply with Section 6.1.5. Remaining or expired drugs should be returned to the sponsor and may not be used for non-participants.

When the investigational drug is transported to study sites, a drug receipt form should be signed by both parties in duplicate, one copy for study sites and the other for the sponsor. When returning remaining drugs and empty packaging, both parties must sign the drug return form. The dispensation and return of every drug should be immediately documented on designated forms.

The CRA is responsible for monitoring the supply, use, and storage of investigational drugs, and disposal of remaining drugs.

7.2.1. Disposal of investigational drug

The sponsor or authorized personnel is responsible for disposing investigational drugs. Drug disposal should be well documented.

7.3. Concomitant Treatment

7.3.1. Permitted concomitant medications

- Topical use of corticosteroids, such as ophthalmic, nasal, intra-articular, and inhaled administrations, are permitted.
- Use of immunosuppressive agents (such as prednisone of > 10 mg/d or an equivalent dose of glucocorticoids) to handle the AEs in the study.

- Prophylactic use of short-term glucocorticoids, such as for the prevention of contrast agent allergy; short-term glucocorticoids that are used to treat non-autoimmune diseases, such as delayed allergic reactions caused by exposure to allergens.
- The use of inactivated seasonal influenza vaccines is allowed; the use of live attenuated vaccines needs to be decided upon discussion with the sponsor.

7.3.2. Prohibited concomitant medications

- Chemotherapy, radiotherapy, hormone therapy, or immunotherapy
- Immunosuppressants;
- Modern TCM preparations approved by the NMPA for anti-tumor treatment;
- Inoculation of live vaccines within 4 weeks before the first dose and during the study. Live vaccines include but are not limited to, rubeola, epidemic parotitis, rubella, chicken pox, yellow fever, rabies, BCG, and typhoid vaccines. Injections of inactivated influenza vaccine for seasonal influenza are permitted, but not live attenuated influenza vaccines for intranasal use;

7.4. Recommendations on the Handling of Immune-Related Adverse Events

Subjects should receive appropriate supportive treatment measures deemed necessary by the investigators. Supportive treatment measures for managing immune-related AEs (irAEs) are listed below, including oral or intravenous corticosteroids and other anti-inflammatory medications when symptoms are not relieved after the use of corticosteroids. Corticosteroids may need to be tapered over several cycles since symptoms may worsen during dose reduction. Other reasons requiring other supportive treatments, such as metastatic disease or bacterial or viral infections, should be ruled out where possible. When the investigators are sure that the AE is related to SHR-1210, the supportive treatment listed below may be followed. Otherwise, the supportive treatment listed below is not required.

1. Diarrhea/Colitis

Subjects should be carefully monitored for signs and symptoms of enterocolitis (such as diarrhea, abdominal pain, hematochezia, or mucus stools, with or without pyrexia) and intestinal perforations (such as peritonitis and intestinal obstruction).

- Subjects with diarrhea/colitis should drink an adequate amount of fluids. Fluids and electrolytes should be administered intravenously if adequate oral intake is not possible. GI consultation and endoscopy should be considered to confirm or rule out colitis for subjects with Grade 2 or greater diarrhea.

- Oral corticosteroids should be prescribed for Grade 2 diarrhea/colitis.
- Subjects with Grade 3 or 4 diarrhea/colitis should be treated with intravenous corticosteroids followed by oral high-dose corticosteroids.
- Corticosteroids should begin to taper after symptoms improve to Grade 1 or lower. Taper will last for no less than 4 weeks.

2. AST, ALT, or bilirubin increased

- Subjects should receive intravenous or oral corticosteroids for Grade 2 events. Liver function should be monitored with an increased frequency until it/they recover(s) to baseline (testing once per week considered).
- Corticosteroids via intravenous route for 24-48 h should be given for Grade 3-4 events.
- Corticosteroids should begin to taper after symptoms improve to Grade 1 or lower. Taper will last for no less than 4 weeks.

3. Hyperthyroidism/hypothyroidism

Thyroid disorder may occur at any time during the course of the treatment period. Monitor changes in subjects' thyroid function (when starting treatment, regularly during the treatment period) as well as clinical signs and symptoms of thyroid disease.

- For subjects with Grade 2 hyperthyroidism, it is recommended to use non-selective beta-blockers (such as propranolol) as initial treatment.
- Subjects with Grade 3-4 hyperthyroidism should receive intravenous corticosteroids followed by oral corticosteroids. Corticosteroids should begin to taper after symptoms improve to Grade 1 or lower. Taper will last for no less than 4 weeks. During the tapering process, appropriate hormone replacement therapy may be required.
- Thyroid hormone replacement therapy may be considered for Grade 2-4 hypothyroidism (such as levothyroxine).

4. Pneumonia

- Subjects with Grade 2 pneumonia should receive systemic corticosteroids. Corticosteroids should begin to taper after symptoms improve to Grade 1 or lower. Taper will last for no less than 4 weeks.
- If subjects receive long-term corticosteroids, antibiotic prophylaxis should be used.

5. Immune-Related Hypophysitis

- Persistent corticosteroid treatment should be used for Grade 2 hypophysitis. Corticosteroids should begin to taper after symptoms improve to Grade 1 or lower. Taper will last for no less than 4 weeks. During the tapering process, appropriate hormone replacement therapy may be required.
- Subjects with Grade 3 or 4 hypophysitis should receive intravenous corticosteroids followed by oral corticosteroids. Corticosteroids should begin to taper after symptoms improve to Grade 1 or lower. Taper will last for no less than 4 weeks. During the tapering process, appropriate hormone replacement therapy may be required.

6. Type I diabetes mellitus

Insulin replacement therapy is recommended for T1DM and Grade 3-4 hyperglycemia accompanied by metabolic acidosis or ketonuria. Then, subjects' blood glucose, and full metabolic panel, urinary ketones, HbA1C, and C-peptide should be evaluated.

7. Renal Failure or Nephritis

- Subjects with Grade 2 events should receive corticosteroids.
- Subjects with Grade 3-4 events should receive systemic corticosteroids.
- Corticosteroids should begin to taper after symptoms improve to Grade 1 or lower. Taper will last for no less than 4 weeks.

8. Infusion Reaction

CTCAE Grade	Clinical Symptom	Clinical Management	SHR-1210 Treatment
Grade 1	Mild and transient reactions	Bedside observation and close monitoring until recovery. Premedications are recommended for subsequent infusion: diphenhydramine 50 mg or equivalent, and/or acetaminophen 325-1000 mg, given at least 30 min before SHR-1210 infusion.	Continue
Grade 2	Moderate reactions requiring treatment or interruption; rapidly resolve after symptomatic treatment (such as antihistamines, non-steroidal)	Intravenous drip infusion of normal saline, IV of diphenhydramine 50 mg or equivalent and/or acetaminophen 325-1000 mg; Bedside observation and close monitoring until recovery. Corticosteroids or bronchodilators can be considered based on clinical needs; The amount of investigational drug infused should be recorded in the original medical record;	Interrupt. Re-administer at 50% of the initial rate after symptoms resolve. If no reaction occurs within 30 min, restore the original infusion rate (100%). Closely monitor. If the symptoms recur, the administration of the current

CTCAE Grade	Clinical Symptom	Clinical Management	SHR-1210 Treatment
	antiphlogistics, anesthetics, bronchodilators, and intravenous fluids)	Premedications are recommended for subsequent infusion: diphenhydramine 50 mg or equivalent, and/or acetaminophen 325-1000 mg, given at least 30 min before SHR-1210 infusion. Use corticosteroids (equivalent to hydrocortisone 25 mg) when necessary.	SHR-1210 dose will be discontinued.
Grade ≥ 3	Grade 3: Severe reaction without rapid recovery with treatment and/or interruption; or symptoms recur after alleviation; or the subject develops sequelae that require hospitalization. Grade 4: life-threatening	Immediately discontinue SHR-1210; Administer normal saline by intravenous drip infusion. • Bronchodilators are recommended: subcutaneous injection of 1:1000 adrenaline solution 0.2-1 mg or slow intravenous infusion of 1:10,000 adrenaline solution 0.1-0.25 mg, and/or diphenhydramine 50 mg + methylprednisolone 100 mg or equivalent by intravenous injection when necessary; • Based on the guidelines for anaphylaxis of study sites; Bedside observation and close monitoring until recovery.	Discontinuation

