10.4. Adverse Event of Special Interest

When an AE of special interest specified in the study protocol occurs, the investigators must fill out the "Report Form of Adverse Events of Special Interest for Hengrui Clinical Studies" and report to the sponsor within 24 h of being notified. If the AE of special interest is also an SAE, the "NMPA Serious Adverse Event Report Form" should also be completed and submitted to the relevant authorities according to the SAE reporting procedure.

- Grade ≥ 3 infusion reaction;
- Grade ≥ 2 diarrhea/colitis, uveitis, and interstitial pneumonia;
- Other Grade ≥ 3 immune-related AEs;
- Any events that meet Hy's Law ($ALT/AST > 3 \times ULN$ accompanied with $TBIL > 2 \times ULN$ and without other causes).

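### An infusion reaction that starts as Grade 2, resolves and recurs on restart falls under two rows of the Section 7.4 table with different treatment consequences

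*Protocol*

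**What the plan says.** The infusion reaction table in Protocol Section 7.4 (item 8) gives, for each CTCAE grade, the symptoms, the clinical management and the action on SHR-1210.

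- **Grade 2, definition:** "Moderate reactions requiring treatment or interruption; rapidly resolve after symptomatic treatment".
- **Grade 2, action:** interrupt, then "Re-administer at 50% of the initial rate after symptoms resolve". If nothing happens within 30 minutes, the full rate is restored. The recurrence instruction begins "If the symptoms recur, the administration of the current" and is split by a page break. Table 2 in Section 7.1.6.1 carries it unbroken: "If the symptoms recur, the administration of the current SHR-1210 dose will be discontinued".
- **Grade 3, definition:** a severe reaction that does not settle rapidly, "or symptoms recur after alleviation; or the subject develops sequelae that require hospitalization".
- **Grade ≥3, action:** "Immediately discontinue SHR-1210; Administer normal saline by intravenous drip infusion", with discontinuation in the treatment column. Table 2 also gives discontinuation for Grade 3-4.

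The grade is used again later. Section 10.4 lists a Grade ≥3 infusion reaction as an adverse event of special interest (AESI), for which the investigator must "report to the sponsor within 24 h of being notified". SAP Section 5.5.2 analyses Grade ≥3 infusion reactions as an AESI. Protocol Section 10.1.2 names NCI-CTCAE V4.03 as the general grading authority.

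**The concern.** The Grade 2 row sends the subject into a restart, and a restart can end in recurrence. The row answers that recurrence with a stop limited to the current dose. One row further down, recurrence after alleviation is itself a criterion for Grade 3, and Grade 3 ends SHR-1210. A site that follows the Grade 2 instruction exactly can therefore arrive at an event that the next row classifies and handles differently.

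Two things depend on which row is read. The first is subject safety: whether a person whose infusion reaction has recurred may be given the drug again or is taken off it. The second is safety reporting: whether the event goes to the sponsor within 24 hours as an AESI and is counted among the Grade ≥3 infusion reactions. The severity summary and the discontinuation reasons (SAP Sections 5.5.2 and 5.2.1) move with it.

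**Working it through.** The plan gives no figure to reproduce here. The check is to follow one event through the tables.

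| Step | Section 7.4, Grade 2 row | Section 7.4, Grade ≥3 row | Table 2 (7.1.6.1) |
|---|---|---|---|
| Moderate reaction, infusion interrupted | Applies | Does not apply | Grade 2 row applies |
| Symptoms resolve, restart at 50% rate | Instructed | – | Instructed |
| Symptoms recur | Stop the current dose | Meets the recurrence criterion for Grade 3 | Grade 2 row: stop the current dose |
| Consequence for SHR-1210 | Limited to that dose | Discontinuation | Grade 2: limited to that dose; Grade 3-4: discontinuation |

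**Is recurrence a criterion of its own?** The alternatives in the Grade 3 definition are separated by semicolons and joined by *or*. On the ordinary reading, recurrence after alleviation is enough by itself.

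**Are the two consequences really different?** Yes. The Grade 2 text limits the stop to the current dose. In Table 2 the Grade 2 row has a resumption condition, while the Grade 3-4 row has discontinuation in the resumption column as well as in the treatment column.

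**Does other text settle the action?** Table 2 does not repeat the Grade 3 recurrence criterion, and no section tells the site to regrade after a recurrence. The note under Table 2 on recurring events concerns Grade 3 events that recur, not a Grade 2 reaction that returns on restart.

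**How many subjects?** The documents give no infusion reaction rate for SHR-1210 and no recurrence rate. An illustration:

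- Reactions: Section 2.1 cites 20% injection-related reactions with another PD-1 antibody. 0.20 × 60 = 12.
- Recurrence on restart, assumed at 10% to 25%: 0.10 × 12 = 1.2 and 0.25 × 12 = 3.0.
- The base of 12 is generous, because the 20% is not restricted to Grade 2. Under Section 7.4, Grade 1 continues and Grade ≥3 discontinues, so neither enters the restart branch. Infusion reaction is also absent from the frequent phase I events listed in Section 2.3. The lower end of the range is therefore 0.
- Effect per subject, if all 60 are in the Safety Set: 1/60 = 1.7 percentage points on the Grade ≥3 infusion reaction rate. Three subjects would be 3/60 = 5.0 points.

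**The case against.** The best defence is that the rows can be read together. The Grade 3 entry opens with a severe reaction and the Grade 2 entry with a moderate one, so severity might govern every alternative and a moderate recurrence might stay Grade 2. A specific instruction for recurrence on restart might also be taken to override a general descriptor. Alternatively, stopping the current dose is simply the first step, after which the event is regraded and the drug discontinued. These readings are possible. The punctuation does not require the first, and no text states the override or the regrading. They also lead to different outcomes, which is the ambiguity itself.

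Three parts of the defence stand and limit the point.

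- A reader might infer that the two rows have opposite consequences and that the Grade 2 row keeps the subject on treatment. The documents do not say so. The premedication advice for later infusions covers Grade 2 reactions generally and is not tied to the recurrence branch. The consequences are different, not opposite.
- A reader might infer that nothing in the protocol governs. That is too broad for the grade, because Section 10.1.2 names an authority, although its text cannot be checked here. What remains open is the treatment action, and how the grading text in Section 7.4 fits with that authority.
- Section 7.1.6.1 requires sponsor consultation when a site departs from Table 2 or meets an unlisted situation. This helps a site that notices the conflict. A site that believes it is following a listed row has no clear reason to call.

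**Conclusion.** The inconsistency is in the text: one safety event has two stated treatment outcomes, and no rule chooses between them. It bears on subject safety and on the handling of one AESI category, and should be corrected.

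The extent is limited. ORR, the sample size and the decision rule are not affected. The number of subjects is likely small: 0 to about 3, resting on another antibody's reaction rate and an assumed recurrence rate of 10% to 25%. The finding does not depend on that range, since a single case raises the question for that subject.

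Two further inferences are not supported. One is that rates would not be comparable across the approximately 15 sites: Protocol Section 12 pools all sites and no between-site comparison is planned. The other is that a subject kept on treatment would fall under the important deviation, listed in SAP Section 5.2.5, of meeting withdrawal criteria without withdrawing. The withdrawal criteria in Protocol Section 5.3 contain no specific infusion reaction rule, although the SAP list is not exhaustive.

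**What to change.** Reconcile the Grade 2 recurrence instruction in Table 2 and in the Section 7.4 table with the Grade 3 definition in Section 7.4, so that recurrence after restart maps to one grade and one treatment consequence. The grade should be consistent with the authority named in Section 10.1.2. Use the same wording in both tables, and apply the resulting grade to AESI reporting under Section 10.4 and to the AESI analysis in SAP Section 5.5.2. Which consequence applies is for the sponsor's clinical team to decide; this review takes no position on it.

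The cost is a small wording amendment, ethics committee approval before implementation (Section 16.3) and notification of the sites. No new data are needed. If dosing has already taken place, recurrences on restart can be traced from source records, since the Grade 2 row requires the amount infused to be recorded, and classified by the single rule.
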